3.1.3 Secondary Objectives (Cohort A and Cohort B)

- To evaluate PFS.
- To compare the treatment planning in DOSIETM with the plan generated in COMSOLTM in Cohort A only.
- To measure changes in tumor pO2, optical properties, and irradiance and fluence in relationship to response.
 - •

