- o At [name] laboratory, both DOSIE[™] and COMSOL[™] will be used to generate treatment planning for 630-nm laser. Each plan will use the same number and location of the fiber placement, diffuser length, and intensity (W/cm). The software packages will be used to compute the irradiance and fluence required to administer our target irradiance of ≥ 8.6 mW/cm² in a significant volume of the target tumor. The plans will also suggest the treatment time to deliver ≥45 J/cm² to a significant volume of the target tumor.
- For each plan, the research team will generate a table showing the light delivery options and percent of tumor volume that will receive the minimal and maximal irradiance and fluence for the physician to review.
- The research team will compare the DOSIETM computation with the COMSOLTM. Although both use same input, the differences in the mesh generation and the solvers used in the simulations could impact the resulted irradiance and fluence. The comparison will include percent of tumor that receive ≥ 8.6 mW/cm² and ≥ 45 J/cm², the irradiance and fluence at the margins, the minimum, average, and maximum irradiance and fluence in 100% of the tumor. If there is disagreement (more than 5% difference) we will use COMSOLTM computation.
- The treating physician will review the plan and either approve or request changes.
 - Several iterations (typically 1-3) may be required until the treating physician approves the plan. The review will be in-person or via secured web-based communication (e.g., password protected Microsoft Teams).
 - Once approved, a detailed description of the plan will be provided via secured e-mail.
- The I-PDT procedure will follow the plan as much as possible, taking into consideration patient safety, and treatment time.
 - \circ Our previous studies suggest that fiber placement within ≤ 10 mm from the planned placement will have insignificant impact on the total light irradiance and fluence in the target tumor.

• The difference between the planned and actual placement of the fibers will be recorded (using EBUS imaging and measurements). These data will be used for post analysis, to calculate the actual light distribution by DOSIE[™] and COMSOL[™].

Extrabronchial tumors that are identified by EBUS will be treated with I-PDT. The laser fiber will be inserted into the tumor using the EBUS-TBN. The I-PDT procedure will follow these steps:

- Curvilinear Endobronchial Ultrasound will be used to identify the tumor.

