12.1.4 Secondary Analysis

For both Cohort 0+A combined and Cohort B progression free survival (PFS) will be defined as the time from date of study treatment to the time of first observed disease progression (modified RECIST 1.1 criteria) at the treated tumor site or death due to any cause. PFS will be summarized using standard Kaplan-Meier methods, with median PFS and specified PFS rates estimated with 95% confidence intervals. The number of bronchoscopies will be summarized descriptively.

For Cohort A only we will measure agreement between DOSIETM and COMSOLTM treatment planning measures in n=18 subjects consisting of light intensity from each fiber (mW, and mW/cm), percent of tumor that receives ≥ 8.6 mW/cm² and ≥ 45 J/cm², the irradiance and fluence at the margins, the min, average and maximum irradiance and fluence in 100% of the tumor using the concordance correlation coefficient (76)(CCC) and Bland-Altman plots (77) for visual displays of agreement. We will calculate the one-sided 95% confidence interval for the CCC using a percentile bootstrap-t approach for each endpoint and we will calculate the 95% confidence interval display. Disagreement on a given measure will be inferred if the estimated CCC is below the lower bound of the one-sided 95% percentile confidence interval.

Tumor response as a function of STAT3 tumor conversion percentages (if possible) will be analyzed using logistic regression adjusted for age and sex.

The data from this trial will inform the design of a prospective Phase IIb randomized trial.

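### The DOSIE–COMSOL rule compares the estimated CCC with the lower limit of its own confidence interval, so in practice it can never conclude disagreement

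*Combined protocol and SAP*

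**What the plan says.** Section 3.1.3 lists the software comparison as a secondary objective: "To compare the treatment planning in DOSIETM with the plan generated in COMSOLTM in Cohort A only". Sections 4.1.3 and 12 repeat it as a secondary endpoint.

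Section 12.1.4 gives the analysis. Agreement is measured on "treatment planning measures in n=18 subjects", covering light intensity per fiber, tumor coverage at the irradiance and fluence thresholds, values at the margins, and the minimum, average and maximum. The statistic is the CCC, with Bland-Altman plots as a visual aid. On the interval it says: "We will calculate the one-sided 95% confidence interval for the CCC using a percentile bootstrap-t approach for each endpoint". The decision rule follows: "Disagreement on a given measure will be inferred if the estimated CCC is below the lower bound of the one-sided 95% percentile confidence interval".

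One other numerical disagreement limit appears, in Section 6.1.2 on treatment planning: "If there is disagreement (more than 5% difference) we will use COMSOLTM computation". It selects the computation for an individual patient's plan. It is not on the CCC scale, and Section 12.1.4 does not refer to it. Section 12.1.6 gives no benchmark, margin or power for the agreement analysis.

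**The concern.** A test of agreement needs something outside the data to compare with: a CCC value below which two planning systems would be judged not interchangeable. Here the comparator is the lower limit of the interval around the estimate itself. That limit comes from the same 18 pairs and is constructed to sit beneath the estimate, so the condition that the estimate "is below the lower bound of the one-sided 95% percentile confidence interval" is not met, whether agreement is excellent or absent.

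This is the only trial-level inferential rule for the objective. Under it, every planning measure would carry the label of no disagreement, and a reader could take that as validation of the newer software. The context makes such a reading likely. Section 1.1.9 says that a research award supports the comparison and that the developer's long-term goal is regulatory approval of DOSIE for treatment planning. Section 12.1.4 says that the trial's data will inform a later randomized trial.

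**Working it through.** **Inputs.** From Section 12.1.4: n = 18 pairs, a one-sided 95% interval, and the rule that disagreement is inferred if the estimated CCC is below the lower limit L. The section names both a percentile and a bootstrap-t method, so both were checked. The plan states no operating characteristic for this rule, so there is no figure of its own to reproduce.

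**Statistic.** CCC = 2·s_xy / (s_x² + s_y² + (x̄ − ȳ)²).

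**What the rule requires.**

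- *Percentile limit.* L is the 5th centile of the resampled CCCs. The estimate is below L only if fewer than about 5% of resampled values lie at or below the estimate. Resampled values scatter around the estimate, so this does not ordinarily happen.
- *Bootstrap-t limit.* L = estimate − t₀.₉₅ × SE, where t₀.₉₅ is the 95th centile of (CCC* − estimate)/SE*. The estimate is below L only if t₀.₉₅ is negative, which needs at least about 95% of resampled values to fall below the estimate. This does not ordinarily happen either.

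**Simulation.** n = 18 pairs, 600 trials per scenario, 500 resamples per trial, jackknife standard error for bootstrap-t. x is standard normal; y has the stated correlation with x and is then scaled and shifted, in units of the SD of x.

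| Correlation | Shift | Scale | Mean estimated CCC | Estimate < percentile L | Estimate < bootstrap-t L |
|---|---|---|---|---|---|
| 0.999 | 0 | 1 | 0.999 | 0/600 | 0/600 |
| 0.99 | 0 | 1 | 0.989 | 0/600 | 0/600 |
| 0.95 | 0 | 1 | 0.941 | 0/600 | 0/600 |
| 0.80 | 0 | 1 | 0.772 | 0/600 | 0/600 |
| 0.50 | 0 | 1 | 0.460 | 0/600 | 0/600 |
| 0 | 0 | 1 | -0.005 | 0/600 | 0/600 |
| -0.50 | 0 | 1 | -0.444 | 0/600 | 0/600 |
| 0.99 | 1 | 1 | 0.625 | 0/600 | 0/600 |
| 0.99 | 3 | 1 | 0.171 | 0/600 | 0/600 |
| 0.99 | 0 | 3 | 0.578 | 0/600 | 0/600 |
| 0.90 (lognormal) | 0.5 | 1 | 0.671 | 0/600 | 0/600 |
| 0 | 2 | 3 | 0.011 | 0/600 | 0/600 |

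The simulated means are close to the formula. For example, with correlation 0.99 and a shift of 3, 2 × 0.99 / (1 + 1 + 9) = 0.18, against 0.171 simulated.

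The total is 12 × 600 = 7,200 trials per method with no firing. Within one scenario, 0 of 600 gives a one-sided 95% upper bound of 1 − 0.05^(1/600) = 0.5% for the firing probability.

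**Edge case.** Firing was found only for almost perfectly inverse data. At correlations of -0.99 and -1 the percentile version fired in roughly 1% to 6% of trials; at -1 the bootstrap-t version did not fire. There the CCC is near its floor of -1, so resampled values can move only upward. This is an artefact of the boundary.

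**Can another reading rescue it?** If the one-sided interval is bounded above instead, its lower end is the minimum of the CCC scale and the rule still cannot fire.

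**The same data against a fixed benchmark.** A benchmark of 0.90 is assumed for illustration only; it is not in the documents.

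- *Agreement concluded if the percentile lower limit exceeds 0.90.* At correlation 0.80: 1 − 1.000 = 0%. At 0.95: 1 − 0.640 = 36%, with repeat runs giving 37% to 40%. At 0.99: 1 − 0.000 = 100%.
- *Disagreement concluded if the percentile upper limit is below 0.90.* This fires in 0.3% of trials at mean CCC 0.94, 57.8% at 0.77, 98.7% at 0.46 and 100% at 0.17.

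Either form separates good from poor agreement. The written rule does not.

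**The case against.** The strongest reply is that the faulty sentence hides little. Section 12.1.4 also calls for the CCC, its interval and Bland-Altman plots for the planning measures, so a CCC near zero would be visible in the same report. No passage makes adoption of DOSIE depend on the verdict. The choice of plan for each patient rests on the 5% rule in Section 6.1.2, which works without the CCC. Both programs receive the same fiber number, positions, diffuser length and intensity, so gross disagreement is unlikely. Finally, a bootstrap limit is not mathematically bound to lie below the estimate.

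Much of this stands as limits on the consequence. The estimates remain valid, patients' plans are not decided by this rule, and effectively never is more exact than never. None of it gives the rule a function. The 5% rule selects a computation patient by patient and supports no trial-level conclusion, and the Bland-Altman plots have no stated acceptance limits. Even if gross disagreement is unlikely, the rule is equally silent at moderate disagreement: it did not fire at a mean CCC of 0.77 or 0.46. The sponsor may have meant to compare the lower limit with a benchmark, but none is given, and one chosen after seeing the data would be post hoc.

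**Conclusion.** The concern holds. As written, the rule for a named secondary objective cannot, for practical purposes, return the one conclusion it is meant to allow. The chance of inferring disagreement was 0 in every scenario from near-perfect agreement to a mean CCC of -0.44, with either bootstrap method. The result rests on the reading that the interval in the rule is the interval for the same CCC, which is the only one Section 12.1.4 defines. The simulations assume normal or lognormal pairs with n = 18, but the argument from how the limits are built does not depend on those distributions beyond the boundary case near -1. The effect is limited to the DOSIE–COMSOL comparison in Cohort A; the primary response tests, PFS and safety monitoring do not use this rule. Within that objective the sentence is wrong and must be corrected before the comparison is analyzed.

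**What to change.** Replace the decision sentence in Section 12.1.4. The sponsor should prespecify an acceptable CCC on technical and clinical grounds, without sight of the comparison data, and conclude agreement on a measure only if the one-sided 95% lower limit exceeds it. Otherwise the report should say that agreement was not shown. If a positive finding of disagreement is also wanted, it should require the one-sided 95% upper limit to be below the same benchmark. Name one interval method, percentile or bootstrap-t. Alongside the CCC, report how many patients exceeded the 5% difference already used in Section 6.1.2.

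This takes one or two sentences and no extra patients or measurements. The cost is that agreement can now fail to be shown: with a 0.90 benchmark and 18 patients, it would be shown in about 36% to 40% of trials at a true CCC of 0.95 and about 100% at 0.99. If the sponsor cannot justify a benchmark, the minimum repair is to delete the rule and report the CCC, its interval and the Bland-Altman limits descriptively, with no verdict on agreement or disagreement.

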12.1.5 Exploratory Analysis

Porfimer sodium retention in the target tumor tissue will be descriptively summarized with mean \pm standard deviations. We will correlate immune biomarkers and tumor response measures using the Spearman correlation of ± 0.63 or larger differences from 0, at 0.80 power and alpha=0.05 (two-sided).

12.1.6 Phase II Sample Size Justification (Cohort A and Cohort B)

Let π equal the proportion of CR+PR responses. The primary analysis, for Cohort A and Cohort B, will consist of a one-sided exact binomial test of H₀: π =0.05 versus H_a: π >0.05 at level α =0.05. Given n=18 subjects and setting power at 0.80 we will be able to detect an alternative response rate of π >0.29. The primary analysis for Cohort B will consist of a one-sided exact binomial test of H0: π =0.30 versus Ha: π >0.30 at level α =0.05. Given n=39 subjects (including n=6 from the Phase I) and setting power at 0.80 we will be able to detect an alternative response rate of $\pi > 0.50$. A secondary analysis of efficacy will utilize an ordinal regression of response (CR, PR, SD, PD) as a function of baseline tumor volume. All key secondary outcomes will be considered suitably continuous will be analyzed with an analysis-of-covariance (ANCOVA) approach regressing change from baseline to three months on the baseline value of the respective measure adjusted for baseline tumor volume, age, and sex. The null hypothesis of interest is H₀: $\beta_0=0,\beta_1=0$ versus H_a: $\beta_0 \neq 0, \beta_1 \neq 0$, where β_0 is the ANCOVA intercept and β_1 is the regression slope, respectively. All tests will be at level α =0.05. Since both the FACT-L based measures and the 6-minute walk measures are likely to be highly cross correlated no adjustments for multiple testing will be considered a priori. For Cohort A and Cohort B, each continuous endpoint and given n=18 subjects we will have 0.80 power to reject the joint null hypothesis if the slope and intercept account for 39% of the overall variation or larger in the given endpoint. For Cohort B, each continuous endpoint and given n=39 subjects we will have 0.80 power to reject the joint null hypothesis if the slope and intercept account for 20% of the overall variation or larger in the given endpoint.

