12.1.3 Primary Phase II Efficacy Analysis

The primary endpoint for Cohort A and Cohort B is the proportion of complete responders (CR) and partial responders (PR) as measured by RECIST v1.1 at 12 ± 1 week after DOSIETM (Cohort A) and COMSOLTM guided I-PDT.

For Cohort A, we hypothesize that the objective tumor response for CR+PR will be at least 29%. We also want to investigate the impact of variation in optical properties, Photofrin® retention, and fiber location perturbation on the objective tumor response. The primary analysis will consist of a one-sided exact binomial test of H₀: π =0.05 versus H_a: π >0.05 at level α =0.05, where π is the proportion of CR+PR responders. For Cohort B, the primary analysis will consist of a one-sided exact binomial test of H₀: π =0.30 versus H_a: π >0.30 at level α =0.05.

Additional clinical efficacy endpoints are: (1) changes from baseline to 3 months in the FACT-L Total Score related subscales (physical well-being, social/family well-being, emotional well-being, functional well-being); (2) the 6-minute walk measures (distance, VO2max, shortness of breath scores). All key clinical efficacy outcomes will be considered suitably continuous will be analyzed with an analysis-of-covariance (ANCOVA) approach regressing change from baseline to three months on the baseline value of the respective measure adjusted for baseline tumor volume, age, and sex.

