12.1.7 Interim Analysis and Criteria for Early Termination of the Study

A futility analysis of efficacy will be carried out for Cohort B after n=20 subjects have completed the trial. A conditional power calculation will inform the decision to continue accrual.

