12.1.9 Safety Monitoring Lead-In (Cohort B)

The safety profile will be measured by recording treatment related AEs that are \geq grade 4 with attribution of 'possible', 'probable', or 'definite', according to the NCI CTCAE v5.0. The safety measures will be evaluated in all patients who received image-guided I-PDT preceded by standard of care p-XRT of 8 Gy x1 for the treating their MCAO. The following decision rules will be followed: (i) If 0/3 AE \geq grade 4's are observed it will be concluded the therapy is safe. (ii) If 1/3 AE \geq grade 4's are observed, enroll 3 more patients for safety evaluation. If 1/6 AE \geq grade 4's are observed it will be concluded the therapy is safe. If \geq 2/6 AE \geq grade 4's are observed it will be concluded that therapy is unsafe. We calculated via Monte Carlo simulation that if the AE \geq grade 4 rate is 20%, 30% and 40% the respective probabilities of declaring the treatment unsafe are 0.26, 0.51 and 0.70.

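### Section 12.1.6 gives the Cohort B primary test two nulls, 0.05 and 0.30; only 0.30 fits the rest of the plan, so the shared 0.05 wording should go

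*Combined protocol and SAP*

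**What the plan says.** Section 12.1.6 states that "The primary analysis, for Cohort A and Cohort B, will consist of a one-sided exact binomial test of" π = 0.05 against π > 0.05 at level 0.05, and supports this with n=18, power 0.80 and a detectable rate of 0.29. It then states: "The primary analysis for Cohort B will consist of a one-sided exact binomial test of" π = 0.30 against π > 0.30 at the same level, with n=39, power 0.80 and a detectable rate of 0.50. Later in the same section, "For Cohort A and Cohort B, each continuous endpoint and given n=18 subjects" introduces a detectable share of variation of 39%, and the next sentence gives Cohort B n=39 and 20%.

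Section 12.1.3 reads differently. It begins "For Cohort A, we hypothesize that the objective tumor response for CR+PR will be at least 29" percent and follows this with the 0.05 null. It then says: "For Cohort B, the primary analysis will consist of a one-sided exact binomial test of" π = 0.30. No other null is assigned to Cohort B there. Section 4.1 gives 18 patients to Cohort A and 39 to Cohort B.

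Section 12.1.7 plans a futility look in Cohort B after 20 patients: "A conditional power calculation will inform the decision to continue accrual". It names no null and no final boundary.

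Section 12.1.9 describes the Cohort B safety lead-in. No grade 4 or higher event in three patients is safe. One in three leads to three more patients. Then one in six is safe and two or more in six is unsafe. For event rates of 20%, 30% and 40% it reports: "We calculated via Monte Carlo simulation" that the "respective probabilities of declaring the treatment unsafe are 0.26, 0.51 and 0.70".

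**The concern.** Read literally, section 12.1.6 gives the primary test of the larger cohort two success criteria. Any Cohort B result from 5 to 16 responders out of 39 is positive under one sentence and negative under the other. The lower bar lies far below the 30% benchmark that Cohort B is meant to beat. In a single-arm study with no concurrent control the null rate is the whole comparison, so a text that supports two nulls leaves room to choose after the data are seen.

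The ambiguity also reaches the interim look. Conditional power is the chance of reaching the final boundary, and section 12.1.7 relies on a boundary that it does not restate.

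**Working it through.** **Inputs.** Nulls 0.05 and 0.30, one-sided level 0.05, n=18 with rate 0.29, n=39 with rate 0.50 (sections 12.1.3 and 12.1.6); look at n=20 (12.1.7); lead-in rule and probabilities (12.1.9).

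**1. Reproduce the plan's sizing.** The cut-off r is the smallest value with P(X ≥ r | n, π₀) ≤ 0.05. Power is P(X ≥ r | n, π₁).

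| Cohort | n | Null | Cut-off | Exact level | Power | Rate detectable with 80% power |
|---|---|---|---|---|---|---|
| A | 18 | 0.05 | 4 | 0.0109 | 0.812 at 0.29 | 0.285 |
| B | 39 | 0.30 | 17 | 0.04998 | 0.832 at 0.50 | 0.491 |

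For 0.30 against 0.50, 39 is the smallest n with exact level at most 0.05 and power at least 0.80 (n=36 gives 0.798, n=38 gives 0.791). Power above 0.80 at n=39 reflects the discreteness of the exact test and is not an error.

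**2. Swap the nulls.** With the 0.05 null at n=39, the cut-off is 5 (exact level 0.0438) and the detectable rate is 0.166, not 0.50. With the 0.30 null at n=18, power at 0.50 is only 0.41. Each pair of n and detectable rate therefore fits one null only: 18 and 0.29 go with 0.05, and 39 and 0.50 go with 0.30.

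**3. Distance between the two bars at n=39.**

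- 0.05 null: 5/39 = 12.8%. At a true rate of 0.30, P(X ≥ 5) = 0.997.
- 0.30 null: 17/39 = 43.6%. At a true rate of 0.30, P(X ≥ 17) = 0.050.

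**4. Effect on the interim look.** As an illustration, take 4 responders in the first 20, leaving 19 patients. The plan gives no assumed future rate, so a range is shown. Reaching 17 needs P(X ≥ 13 | 19, p); reaching 5 needs P(X ≥ 1 | 19, p).

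| Future rate p | Conditional power, 17/39 | Conditional power, 5/39 |
|---|---|---|
| 0.20 (observed) | <0.0001 | 0.986 |
| 0.30 | 0.0006 | 0.999 |
| 0.50 | 0.08 | 1.00 |

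**5. Lead-in probabilities (minor).** Let q = 1 − p. The written rule reaches unsafe only through one event in three followed by at least one in the next three: 3pq²(1 − q³). It does not say what follows two or three events in the first three. If those count as unsafe, the total is 1 − q³ − 3pq⁵. At p = 0.20 this is 1 − 0.512 − 0.197 = 0.291.

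| p | 1/3, then ≥2/6 | 2 or 3 of first 3 | Total | Stated |
|---|---|---|---|---|
| 0.20 | 0.187 | 0.104 | 0.291 | 0.26 |
| 0.30 | 0.290 | 0.216 | 0.506 | 0.51 |
| 0.40 | 0.339 | 0.352 | 0.691 | 0.70 |

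The stated 0.51 and 0.70 are approached only when the unstated branch is included (0.70 against 0.691 allows for simulation error). The stated 0.26 matches neither version. The number of simulation runs is not given. The top of the rounding range, 0.265, lies 1.8 standard errors below 0.291 with an assumed 1,000 runs, 2.6 with 2,000 and 5.8 with 10,000.

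**The case against.** The strongest reply is that the documents already resolve the conflict. Section 12.1.3, which governs the analysis, ties Cohort B to 0.30. The second sentence in section 12.1.6 is specific to Cohort B, and the 0.05 sentence carries the Cohort A size and the Cohort A hypothesis. No figure for Cohort B uses 0.05. On this view it is a drafting slip, and the 99.7% against 5.0% contrast needs an analyst who ignores two clearer statements. All of this is right about what was intended. It does not remove the sentence, which still names a lower primary bar for Cohort B, and a primary decision rule should not depend on the reader's inference.

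The 4/20 case is hypothetical, and section 12.1.7 would still lack a futility threshold and an assumed future rate after the correction. That is fair: the example shows only that the look depends on which boundary is used.

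On the lead-in, two events in the first three patients already meet the condition of two or more in six, so the missing branch can be inferred, and a small simulation could account for 0.26. Both points stand. They are why this item is rated low.

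**Conclusion.** The concern holds. Section 12.1.6 states two primary nulls for Cohort B. The 0.30 null is the intended one, and the shared reference in the 0.05 sentence is best read as a carry-over. That reading is an inference, but section 12.1.3, the cohort sizes and the exact power calculation all support it. At n=39 the two bars are 12 responders apart (5 against 17). Correction is needed because the error sits in the primary success criterion.

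The binomial sizing of both cohorts is sound. That statement covers only the exact-test arithmetic, not the inclusion of six Phase I patients among the 39. The repeated wording in the n=18 and 39% sentence changes no decision rule.

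The lead-in discrepancy is minor. If two or three events in the first three patients count as unsafe, the exact probability at a 20% event rate is 0.29 against the stated 0.26, so the rule stops slightly more often than the plan says.

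**What to change.** In section 12.1.6, delete *and Cohort B* from the sentence with the 0.05 null and from the sentence with n=18 and 39%. Cohort B then has one null, 0.30, and one continuous-endpoint statement, n=39 and 20%.

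Optionally, state the cut-offs (4 or more of 18 for Cohort A, 17 or more of 39 for Cohort B) and say in section 12.1.7 that conditional power refers to the Cohort B boundary.

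Separately, in section 12.1.9, reconcile the written lead-in rule with the branch that its figures assume, and replace the simulated probabilities with exact values for the reconciled rule.

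The cost is one phrase removed from two sentences, plus a wording and figure correction in section 12.1.9. Sample size and data collection do not change.

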3.1.2 Primary Phase II Objectives (Cohort A and Cohort B)

- To assess the tumor response to treatment.
- To observe changes in well-being.

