4.1.2 Primary Phase II Endpoints (Cohort A and Cohort B)

- Objective tumor response (CR, PR, PD, and SD)
- The FACT-L Total Score related subscale
- 6-minute walk measures.

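### The planned FACT-L and six-minute-walk test can be significant through regression to the mean alone, so it cannot show that patients' scores changed

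*Combined protocol and SAP*

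**What the plan says.** Section 12.1.3 analyses the FACT-L and walk measures by ANCOVA, "regressing change from baseline to three months on the baseline value of the respective measure adjusted for baseline tumor volume, age, and sex". Section 12.1.6 repeats the model and makes the null joint: intercept (beta-0) and regression slope (beta-1) both zero, each measure tested at 0.05 with no multiplicity adjustment. The power statements use the same null. At n=18, "we will have 0.80 power to reject the joint null hypothesis if the slope and intercept account for 39% of the overall variation"; at n=39 the condition is "if the slope and intercept account for 20% of the overall variation or larger in the given endpoint".

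The cohorts are single-arm, so no group term carries a treatment effect. The plan gives no separate test or estimate of mean change, no coding or centring of baseline or covariates, and no baseline-to-follow-up correlation or SD.

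The status of these measures varies. Section 3.1.2 has as a primary Phase II objective "To observe changes in well-being". Section 4.1.2 lists "The FACT-L Total Score related subscale" and the walk measures as primary endpoints, and the opening of Section 12 does the same. Section 12.1.3 introduces them with "Additional clinical efficacy endpoints are", and Section 12.1.6 writes "All key secondary outcomes will be considered suitably continuous".

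**The concern.** The question is whether well-being and walking capacity changed on average. The joint null says something else: that change averages zero and is also unrelated to where the patient started. Patients with low baseline scores tend to rise and those with high scores tend to fall through ordinary within-patient variability, so the second part is normally false even when the mean is flat.

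A significant result could therefore be reported as a change in patients when mean scores did not move. This is the only hypothesis test planned for a primary objective of a palliative trial, and Section 12.1.4 says the data will inform a randomized Phase IIb trial. The power statement has the same weakness: a share of variation does not tell the reader what change in well-being the trial can detect.

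**Working it through.** **1. The plan's own power figures.** Noncentral F, 2 numerator df, alpha 0.05, noncentrality n × R²/(1-R²).

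- n=18, R²=0.39: 18 × 0.39/0.61 = 11.51. Power is 0.788 with 15 error df and 0.793 with 16, so the stated 0.80 is reproduced approximately. With the three covariates also fitted (13 df) it is 0.774.
- n=39, R²=0.20: 39 × 0.20/0.80 = 9.75. Power is 0.769; 0.80 needs R² of about 0.212 or n=42.

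The arithmetic is close. The fault is in the hypothesis being powered.

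**2. What the null implies when the mean has not moved.** Let both time points have mean μ and SD σ, with correlation r. Leaving the covariates aside:

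- slope = (rσ² - σ²)/σ² = r - 1
- intercept = (1 - r)μ
- variance of change = 2σ²(1 - r)
- share of variation due to baseline = (1 - r)²σ² / [2σ²(1 - r)] = (1 - r)/2

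That share is 5% at r=0.9, 15% at 0.7, 20% at 0.6 and 25% at 0.5. Cohort B's 20% is reached at r = 1 - 2 × 0.20 = 0.60. Cohort A's 39% would need r = 1 - 2 × 0.39 = 0.22.

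**3. Rejection rates with no mean change.** Simulation, 20,000 trials per cell. The joint F test compares the full model (intercept, baseline, volume, age, sex) with volume, age and sex only. Assumed, since the documents do not supply them: r; equal SDs; baseline mean 4 SD and mean age 6.5 SD above zero; lognormal tumor volume; sex 50:50; complete data.

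| r | Joint test, n=18 | Joint test, n=39 | Paired t, both n |
|---|---|---|---|
| 0.9 | 10% | 20% | about 5% |
| 0.8 | 16% | 38% | about 5% |
| 0.7 | 23% | 56% | about 5% |
| 0.6 | 32% | 71% | about 5% |
| 0.5 | 41% | 83% | about 5% |

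Centring the covariates changes these by less than one point. Repeat runs, including runs with baseline 90 ± 17 and age 66 ± 9, agreed within about two points.

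**4. Response to a real gain.** Assumed mean gain of 0.5 baseline SD, r=0.7.

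| Test | n=18: no gain to gain | n=39: no gain to gain |
|---|---|---|
| Joint, covariates uncentred | 23-24% to 24-26% | 56% to 59% |
| Joint, covariates centred | 23-24% to 68-76% | 56% to 99% |
| Paired t | 5% to 74-75% | 5% to 97-98% |

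With uncentred covariates the comparison model still contains age, which is nearly constant relative to its distance from zero and absorbs most of a mean shift. Centred coding restores sensitivity, but the no-gain rejection rate stays inflated, so the two causes of rejection remain mixed.

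**5. Detectable mean change, paired t, two-sided 5%, power 0.80.** From the noncentral t: 0.701 SD of change at n=18 and 0.460 at n=39. SD of change = σ√[2(1-r)], so for r from 0.9 to 0.5 this is 0.31 to 0.70 baseline SD at n=18 and 0.21 to 0.46 at n=39.

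**The case against.** The strongest objection is that the size depends on more than r. In general the slope is r × k - 1, where k is the follow-up SD divided by the baseline SD, so the null holds when k = 1/r exactly. With no mean change, k=1.1 and r=0.9 gave 4.5% (n=18) and 5.5% (n=39); k=1.25 and r=0.7 gave 6.9% and 10.2%. In the other direction, k=0.8 and r=0.7 gave about 63% and 97%. This stands as a limit on the size: the table above is the equal-SD case. It does not rescue the test, whose validity would depend on an SD ratio that the plan neither states nor controls.

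Second, Section 12.1.3 names response rate as the primary endpoint, and no decision rule uses FACT-L or walking. That is fair, and the exact binomial test is untouched. But Sections 4.1.2 and 12 list these measures as primary, and the test would be wrong for mean change under either status.

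Third, the joint null is a coherent hypothesis and the plan does not say that a rejection will be read as improvement. True, but nothing else is planned that would answer the well-being objective.

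Fourth, centring baseline at the sample mean and testing the intercept alone would keep the model. It removes most of the fault, but its standard error treats the baseline mean as fixed: type I error was 5-9% with equal SDs and 10-12% at k=0.8. A paired test is cleaner.

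**Conclusion.** The concern holds and should be corrected before analysis. With similar SDs at the two times, the joint null is false for any r below 1, so a rejection does not show that mean well-being or walking changed. For assumed r of 0.9 to 0.5, equal SDs and complete data, rejection with no mean change is about 10-41% at n=18 and 20-83% at n=39, against a nominal 5%. The exact rates depend on r and on the SD ratio, neither of which the documents give; the defect does not depend on a particular value. The weak response to a real gain is a further problem only if covariates are left uncentred, which is how the plan reads as written.

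**What to change.** In Sections 12.1.3 and 12.1.6:

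- Replace the joint null with mean change = 0, tested in each cohort by a one-sample (paired) t test. Drop the slope from the hypothesis.
- Report mean change with its 95% confidence interval and direction for each measure.
- Restate the 0.80 power (two-sided 5%) as a detectable mean change: 0.70 SD of change at n=18 and 0.46 SD at n=39. These assume every patient has both values; if fewer are expected at three months, give the figure for that number.
- If the ANCOVA is kept, label it supportive and prespecify the covariate coding. Its intercept is a correct test of mean change only when baseline is centred at the true population mean. A fixed centre 0.5 SD off gave type I error of 6-15% at n=18 and 9-33% at n=39 for r from 0.9 to 0.5.
- Give these measures one status, primary or secondary, in Sections 4.1.2, 12, 12.1.3 and 12.1.6.

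A separate minor point: the subscales named in Section 12.1.3 ("physical well-being, social/family well-being, emotional well-being, functional well-being") omit the FACT-L Additional Concerns score, although Appendix D collects it. Add it to the list.

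The cost is protocol and SAP wording and a new power sentence. No new data are needed.
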